## 6.1 Serious Adverse Events

A *Serious Adverse Event (SAE)* is any untoward medical occurrence that at any dose:

- results in death
- is life-threatening (defined as an event in which the participant was at risk of death at the time of the event; it does not refer to an event which hypothetically might have caused death if it were more severe)
- requires inpatient hospitalization or causes prolongation of existing hospitalization (see **NOTE** below)
- results in persistent or significant disability/incapacity
- is a congenital anomaly/birth defect
- is an important medical event (defined as a medical event(s) that may not be immediately life-threatening or result in death or hospitalization but, based upon appropriate medical and scientific judgment, may jeopardize the participant or may require intervention [eg, medical, surgical] to prevent one of the other serious outcomes listed in the definition above.) Examples of such events include, but are not limited to, intensive treatment in an emergency room or at home for allergic bronchospasm, blood dyscrasias or convulsions that do not result in hospitalization.) Potential drug-induced liver injury (DILI) is also considered an important medical event. (See [Section 6.6](#) for the definition of potential DILI.)

Suspected transmission of an infectious agent (eg, pathogenic or nonpathogenic) via the study drug is an SAE.

Although pregnancy, overdose, cancer, and potential DILI are not always serious by regulatory definition, these events must be handled as SAEs. (See Section 6.1.1 for reporting pregnancies.)

**NOTE:**

The following hospitalizations are not considered SAEs in BMS clinical studies:

- a visit to the emergency room or other hospital department < 24 hours, that does not result in admission (unless considered an important medical or life-threatening event)
- elective surgery, planned prior to signing consent
- admissions as per protocol for a planned medical/surgical procedure
- routine health assessment requiring admission for baseline/trending of health status (eg, routine colonoscopy)
- medical/surgical admission other than to remedy ill health and planned prior to entry into the study. Appropriate documentation is required in these cases
- admission encountered for another life circumstance that carries no bearing on health status and requires no medical/surgical intervention (eg, lack of housing, economic inadequacy, caregiver respite, family circumstances, administrative reason)
- Admission for administration of anticancer therapy in the absence of any other SAEs (applies to oncology protocols)

### **6.1.1      *Serious Adverse Event Collection and Reporting***

Sections 5.6.1 and 5.6.2 in the IB represent the Reference Safety Information to determine expectedness of SAEs for expedited reporting.

- Following the participant's written consent to participate in the study, all SAEs, whether related or not related to study drug, must be collected, including those thought to be associated with protocol-specified procedures. All SAEs must be collected that occur during the screening period and within      days of discontinuation of dosing. However, any SAE occurring after the start of a new treatment that is suspected to be related to study treatment by the investigator will be reported.
- For participants assigned to treatment and never treated with study drug, SAEs should be collected for 30 days from the date of treatment assignment.
- The investigator must report any SAE that occurs after these time periods and that is believed to be related to study drug or protocol-specified procedure (eg, a follow-up skin biopsy).
- Medical occurrences that begin before the start of study treatment but after obtaining informed consent will be recorded on the appropriate section of the eCRF module.
- All SAEs will be recorded and reported to Sponsor or designee within 24 hours.

- The investigator will submit any updated SAE data to the sponsor or designee within 24 hours of updated information being available.

An SAE report must be completed for any event where doubt exists regarding its seriousness.

If the investigator believes that an SAE is not related to study drug, but is potentially related to the conditions of the study (such as withdrawal of previous therapy or a complication of a study procedure), the relationship must be specified in the narrative section of the SAE Report Form.

SAEs, whether related or not related to study drug, and pregnancies must be reported to BMS or designee within 24 hours of awareness of the event. SAEs must be recorded on the SAE Report Form; pregnancies on a Pregnancy Surveillance Form (electronic or paper forms). The preferred method for SAE data reporting collection is through the eCRF. The paper SAE/pregnancy surveillance forms are only intended as a back-up option when the eCRF system is not functioning. In this case, the paper forms are to be transmitted via email or confirmed facsimile (fax) transmission to:

**SAE Email Address:** Refer to Contact Information list.

**SAE Facsimile Number:** Refer to Contact Information list.

For studies capturing SAEs through electronic data capture (EDC), electronic submission is the required method for reporting. In the event the electronic system is unavailable for transmission, paper forms must be used and submitted immediately. When paper forms are used, the original paper forms are to remain on site.

**SAE Telephone Contact** (required for SAE and pregnancy reporting): Refer to Contact Information list.

If only limited information is initially available, follow-up reports are required. (Note: Follow-up SAE reports must include the same investigator term(s) initially reported.)

If an ongoing SAE changes in its intensity or relationship to study drug or if new information becomes available, the SAE report must be updated and submitted within 24 hours to BMS (or designee) using the same procedure used for transmitting the initial SAE report.

All SAEs must be followed to resolution or stabilization.

## **6.2 Nonserious Adverse Events**

A *nonserious adverse event* is an AE not classified as an SAE.

### **6.2.1 Nonserious Adverse Event Collection and Reporting**

The collection of non-serious AE (with the exception of non-serious AEs related to SARS-CoV-2 infection) information should begin at initiation of study treatment and continue during the treatment period and for a minimum of 100 days following discontinuation of study treatment. Non-serious AE information should also be collected from the start of a placebo lead-in period or other observational period intended to establish a baseline status for the participants. All AEs (SAEs and non-serious AEs) associated with confirmed or suspected SARS-CoV-2 infection must

be collected from the date of the participant's written consent until 100 days following discontinuation of dosing.

After the initial AE/SAE report, the investigator is required to proactively follow each participant at subsequent visits/contacts. All SAEs, and non-serious AEs of special interest and AEs (SAEs and non-serious AEs) associated with confirmed or suspected SARS-CoV-2 infection will be followed until resolution, until the condition stabilizes, until the event is otherwise explained, until the event is deemed irreversible, or until the participant is lost to follow-up (as defined in [Section 3.6.2](#)), or for suspected cases, until SARS-CoV-2 infection is ruled out. All identified non-serious AEs must be recorded and described on the non-serious AE page of the CRF (paper or electronic).

Completion of supplemental CRFs may be requested for AEs and/or laboratory abnormalities that are reported/identified during the course of the study.

### **6.3        Laboratory Test Result Abnormalities**

The following laboratory test result abnormalities should be captured on the nonserious AE CRF page or SAE Report Form (electronic) as appropriate. Paper forms are only intended as a back-up option when the electronic system is not functioning.

- Any laboratory test result that is clinically significant or meets the definition of an SAE
- Any laboratory test result abnormality that required the participant to have study drug discontinued or interrupted
- Any laboratory test result abnormality that required the participant to receive specific corrective therapy

It is expected that wherever possible, the clinical rather than laboratory term would be used by the reporting investigator (eg, anemia versus low hemoglobin value).

#### **6.3.1      Clinical Safety Laboratory Assessments**

Hematology - CBC	
Hemoglobin	
Hematocrit	
Total leukocyte count, including differential	
Platelet count	
Chemistry	
Aspartate aminotransferase (AST) Alanine aminotransferase (ALT) Total bilirubin (Direct Bili if T.Bili > ULN) Alkaline phosphatase (ALP) Lactate dehydrogenase (LDH) Creatinine Blood Urea Nitrogen (BUN) or serum UREA Glucose	Albumin Total protein Sodium Potassium Chloride Calcium Magnesium

Amylase, Lipase - on treatment	TSH, with reflexive fT3 and fT4 if TSH is abnormal - on treatment
Serology	
Hepatitis B/C, (HBV sAG, HCV antibody or HCV RNA), - screening only	
HIV1/2 antibody-screening only	
Other Analyses	
Pregnancy test (WOCBP only: minimum sensitivity 25 IU/L or equivalent units of HCG).	
Follicle stimulating hormone (FSH) screening - only required to confirm menopause in women < age 55)	

Abbreviations: CBC = complete blood count; HBVsAG = hepatitis B surface antigen; HCG = human chorionic gonadotropin; HCV = hepatitis C virus; HIV = human immunodeficiency virus; IU = international unit; L = liter; RNA = ribonucleic acid; fT3 = free triiodothyronine; fT4 = free thyroxine; TSH = thyroid-stimulating hormone; ULN = upper limit normal; WOCBP = women of childbearing potential.

## 6.4 Pregnancy

If, following initiation of the investigational product, it is subsequently discovered that a study participant is pregnant or may have been pregnant at the time of study exposure, including during at least 5 half-lives after product administration, the investigator must immediately notify the BMS medical monitor/designee of this event and complete and forward a Pregnancy Surveillance Form to the BMS designee within 24 hours of awareness of the event and in accordance with SAE reporting procedures described in [Section 6.1.1](#).

In most cases, the study drug will be permanently discontinued in an appropriate manner (eg, dose tapering if necessary for participant safety). Please call the BMS Medical Monitor within 24 hours of awareness of the pregnancy.

The investigator must immediately notify the BMS medical monitor or designee of this event and complete and forward a Pregnancy Surveillance Form to BMS (or designee) within 24 hours of awareness of the event and in accordance with SAE reporting procedures described in Section 6.1.1.

Follow-up information regarding the course of the pregnancy, including perinatal and neonatal outcome, and where applicable, offspring information must be reported on the Pregnancy Surveillance Form.

Any pregnancy that occurs in a female partner of a male study participant should be reported to BMS. Information on this pregnancy will be collected on the Pregnancy Surveillance Form.

## 6.5 Overdose

An overdose is defined as the accidental or intentional administration of any dose of a product that is considered both excessive and medically important. All occurrences of overdose must be reported as an SAE (see Section 6.1.1 for reporting details.).

## **6.6 Potential Drug Induced Liver Injury**

Wherever possible, timely confirmation of initial liver-related laboratory abnormalities should occur prior to the reporting of a potential DILI event. All occurrences of potential DILIs, meeting the defined criteria, must be reported as SAEs (see [Section 6.1.1](#) for reporting details).

Potential DILI is defined as:

1. Aminotransaminases (AT) (ALT or AST) elevation > 3 times ULN

AND

2. Total bilirubin > 2 times ULN, without initial findings of cholestasis (elevated serum alkaline phosphatase),

AND

3. No other immediately apparent possible causes of AT elevation and hyperbilirubinemia, including, but not limited to, viral hepatitis, pre-existing chronic or acute liver disease, or the administration of other drug(s) known to be hepatotoxic.

## **6.7 Other Safety Considerations**

Any significant worsening noted during interim or final physical examinations, electrocardiogram, x-ray filming, or any other potential safety assessment required or not required by protocol should also be recorded as a nonserious or serious AE, as appropriate, and reported accordingly.

## **7 DATA MONITORING COMMITTEE AND OTHER EXTERNAL COMMITTEES**

For part 2, a BICR will be used for determination of BICR-assessed ORR and other efficacy endpoints. Details of BICR responsibilities and procedures will be specified in the BICR charter. Images will be submitted to an imaging third-party vendor for central review. Sites will be trained prior to enrolling the first study patient. Imaging acquisition guidelines and submission process will be outlined in the Study Imaging Manual to be provided by the vendors. Refer to [Section 5.4](#) Imaging Assessment for the Study for further details.

## **8 STATISTICAL CONSIDERATIONS**

### **8.1 Sample Size Determination**

#### **8.1.1 Part 1**

With 9 participants in each arm, if 0, 1, 2, or 3 participants experienced DLTs, the upper limit of the one-sided exact 90% CI for the true DLT rate will be less than 23%, 37%, 49%, and 60% respectively. The calculations are based on the Clopper-Pearson method for the exact confidence intervals.

#### **8.1.2 Part 2**

With an estimated discrepancy rate of 25% between local and repeating testing in central lab for MSI/MMR status, it is expected that approximately 33 participants with MSI-H/dMMR mCRC

determined by local testing will be treated in the study. A sample size of 33 will allow the lower bound of one-sided 95% CI excluding 35% when the observed ORR is 50% in the nivolumab/ipilimumab combination arm. The 35% ORR is expected for local diagnosed MSI-H/dMMR mCRC patients treated with PD-1 inhibitor monotherapy. This sample size will also provide at least 90% power to demonstrate statistical difference with historical ORR of 5% for TKI monotherapy in a similar setting at a two-sided alpha of 0.05.

Based on the estimated discrepancy rate between local and central MSI/MMR testing, of 33 treated participants, approximately 25 participants will have their MSI-H/dMMR status confirmed by repeating central lab testing. During the study, the discrepancy rate will be monitored in an ongoing basis, and study accrual may continue beyond 33 if the discrepancy rate exceeds 25%.

Due to challenges with enrollment, the enrollment for Part 2 was closed after 9 participants were treated, out of the 33 participants planned.

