whose disease progressed after  $\geq 1$  prior regimen (CA209032). In NSCLC patients (CA209012), both combination regimens resulted in high discontinuation rates (up to 39%); therefore, multiple alternative schedules were evaluated. Nivolumab 3 mg/kg combined with more extended ipilimumab dosing (1 mg/kg, every 6 weeks [Q6W] or every 12 weeks [Q12W]) was well tolerated, with similarly low discontinuation rates as monotherapy (10%, 5% respectively vs 10%) and promising response rates of 31-39% (48% in PD-L1+). Nivolumab in combination with ipilimumab has demonstrated remarkable benefit for several solid tumor types, including previously treated MSI-H/dMMR metastatic CRC (mCRC). CA209142 is a Phase 2, open-label, multi-center trial of nivolumab monotherapy and nivolumab in combination with other agents in subjects whose colorectal tumors have defects in the deoxyribonucleic acid (DNA) mismatch repair system (MSI-H/dMMR) or in subjects whose colorectal tumors have proficient mismatch repair (pMMR/non-MSI-H). Preliminary evidence from the nivolumab plus ipilimumab cohort (n = 119) in study CA209142 demonstrated additional clinical improvement of this combination in MSI-H mCRC patients over the cohort of subjects treated with nivolumab monotherapy (n = 74) beyond second-line (2L) of treatment. At data cutoff of September 2021, the median follow-up in the nivolumab plus ipilimumab combination therapy cohort was 64.0 months (range 60.0 to 75.8 months). The objective response rate (ORR) per investigator was achieved in 65% (95% confidence interval [CI]: 55, 73) of subjects, including 17% of subjects who demonstrated complete response (CR). This was numerically higher than the ORR observed in the cohort of 74 subjects who received nivolumab monotherapy (39%, 95% CI: 28, 51) in the same study with median follow-up of 70.0 months. Thus, nivolumab plus ipilimumab combination therapy provided a numerically higher ORR, including CR, and disease control rate (DCR) relative to nivolumab monotherapy during a similar follow-up period. The improved ORR with nivolumab plus ipilimumab combination therapy was translated to the numerically improved progression-free survival (PFS) and OS rates over nivolumab monotherapy. In the combination cohort, Grade 3 to 4 treatment-related adverse events (AEs) occurred in 32% of patients and were manageable.

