### **8.4.2.2 Part 2**

#### **Primary Endpoint Methods**

The BICR-assessed ORR will be summarized. A response-rate estimate and corresponding two-sided exact 95% CI using the Clopper-Pearson method will be provided. BICR-assessed ORR will be further characterized by the rate of CR and PR.

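### Is the Part 2 precision statement (33 participants, lower bound above 35% at 50% observed ORR) unclear because it names no interval method or responder count?

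*Combined protocol and SAP*

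**What the plan says.** For Part 2, Section 8.1.2 states: "A sample size of 33 will allow the lower bound of one-sided 95% CI excluding 35% when the observed ORR is 50" percent. The Synopsis repeats this under Sample Size. The benchmark is explained next: "The 35% ORR is expected for local diagnosed MSI-H/dMMR mCRC patients treated with PD-1 inhibitor monotherapy". A second criterion follows: "This sample size will also provide at least 90% power to demonstrate statistical difference with historical ORR of 5% for TKI monotherapy". The section closes by recording that "the enrollment for Part 2 was closed after 9 participants were treated, out of the 33 participants planned".

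Section 8.1.1, directly above, is more explicit for Part 1. It works by count, "With 9 participants in each arm, if 0, 1, 2, or 3 participants experienced DLTs", and adds: "The calculations are based on the Clopper-Pearson method for the exact confidence intervals".

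For the Part 2 primary endpoint, Section 8.4.2.2 plans a descriptive analysis: "A response-rate estimate and corresponding two-sided exact 95% CI using the Clopper-Pearson method will be provided". It contains no test against 35% and no one-sided bound.

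**The concern.** The two sample-size paragraphs are adjacent and are not written to the same standard. Part 1 gives counts and a method, and Part 2 gives neither. The gap seems to have numerical content, because 50% of 33 is not a whole number of participants and common methods fall on either side of 35% at that nominal value. The one Part 2 interval whose method is named is two-sided, and applying it to the planning sentence gives a different answer. After closure at 9, the only PD-1 monotherapy benchmark in the sample-size text has no counterpart for the number actually treated.

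If this held, a reader could not reproduce the basis for 33, and two readers could disagree on whether a given result clears 35%.

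**Working it through.** **Inputs.** Section 8.1.2: n = 33, one-sided 95%, benchmark 35%, observed ORR 50%, and 9 participants treated. Section 8.4.2.2: two-sided exact 95% interval. Wald and Wilson are brought in only for comparison, since the documents name neither.

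**Formulas for the one-sided 95% lower bound** (x responders, p = x/n, z = 1.645):
- Clopper-Pearson: the 5th percentile of a Beta(x, n − x + 1) distribution.
- Wald: p − z√(p(1 − p)/n).
- Wilson: [p + z²/(2n) − z√(p(1 − p)/n + z²/(4n²))] / (1 + z²/n).

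**The plan's figure.** 0.50 × 33 = 16.5, so the smallest observable count at or above 50% is 17 (17/33 = 51.5%). The Clopper-Pearson bound there is the 5th percentile of Beta(17, 17), or 36.1%, which excludes 35%. Wald at exactly 50% gives 0.50 − 1.645 × √(0.25/33) = 0.50 − 0.143 = 35.7%, which also excludes it. The statement is reproduced either way.

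**Does the method matter at n = 33?**

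| Responders | Clopper-Pearson | Wald | Wilson | Above 35%? |
|---|---|---|---|---|
| 16 (48.5%) | 33.3% | 34.2% | 34.8% | none |
| 16.5 (50%, cannot occur) | 34.7% | 35.7% | 36.2% | split |
| 17 (51.5%) | 36.1% | 37.2% | 37.6% | all |

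The methods disagree only in the row that cannot be observed. The same cut between 16 and 17 appears with continuity-corrected Wald and Wilson, mid-P, Agresti-Coull and Jeffreys bounds: the highest of all eight at 16/33 is 34.8%, and the lowest at 17/33 is 35.7%. The exact binomial tail agrees. At a true rate of 35%, the chance of 17 or more responders is 0.0377, below 0.05, and of 16 or more it is 0.0768, above 0.05.

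**Which method do the documents use?** Every binomial proportion interval for which they name a method is Clopper-Pearson: the Part 1 DLT bounds (Section 8.1.1 and Synopsis), the Part 1 ORR (Section 8.4.2.1 and Synopsis), and the Part 2 ORR and DCR (Section 8.4.2.2 and Synopsis). The Part 1 figures confirm it: one-sided 90% exact upper bounds for 0 to 3 of 9 are 22.6%, 36.8%, 49.0% and 59.9%, which round to the printed 23%, 37%, 49% and 60%.

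**The two-sided interval.** Its lower limit is 33.5% at 17/33 and 36.4% at 18/33. That is a different quantity, with 2.5% in the lower tail instead of 5%. The documents attach the 35% property to the one-sided bound only, so there is no conflict.

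**The second criterion.** With 2.5% in the upper tail, the exact rule against 5% is 5 or more of 33 (tail probability 0.0230). The alternative ORR is not restated there. Power is 94% if it is 25% and above 99.9% if it is 50%, so this support for 33 does not involve the 35% sentence.

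**At n = 9.** One-sided bounds for Clopper-Pearson, Wald and Wilson are 25.1%, 28.3% and 30.4% at 5/9; 34.5%, 40.8% and 39.8% at 6/9; and 45.0%, 55.0% and 50.4% at 7/9. Only 6/9 splits, and only because two methods outside the plan are brought in. Under the exact method there is one answer, 34.5%.

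**The case for a change.** The best case for the concern is that the protocol sets its own standard in Section 8.1.1 and misses it a few lines later. Read literally, at exactly 50%, the sentence is true under Wald and false under the exact formula. Someone who borrows the only interval named for Part 2 takes its sidedness too and arrives at 18 responders instead of 17. And at n = 9 the one count on which methods split, 6/9 (66.7%), is the count nearest the rate cited in Section 1.1.1: "The objective response rate (ORR) per investigator was achieved in 65% (95% confidence interval [CI]: 55, 73) of subjects".

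Part of this stands. The method and the count are missing from the sentence in both places, and that Clopper-Pearson was used at planning is an inference, not something the documents say. The rest does not carry. An observed 50% is an ordinary rounded planning value, and the beta formula at half a responder describes no possible result. Taking over the two-sided interval means overriding the word one-sided in the sentence itself. The plan states no property against 35% for 9 participants. The 65% is an investigator-assessed rate from another study, while the primary endpoint here is assessed by BICR, and the interval that would be reported at 6/9, 29.9% to 92.5%, is fully determined by Section 8.4.2.2.

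**Conclusion.** The concern does not hold. The sentence is correct as a one-sided statement. The cut falls between 16 and 17 of 33 under every method tried, so leaving the method unnamed affects no result that could have been observed at the planned size. The sentence describes precision at a given observed rate. It is not a decision rule: no test, threshold or one-sided bound against 35% enters the analysis, and the reported interval is specified in full. Closure at 9 of 33 is disclosed in the same section, and the rationale for Amendment 07 already says the study will not meet its scientific objectives.

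What remains is a possible wording addition to a planning rationale that events have overtaken. It would change no sample size, estimate, interval or conclusion.

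This rests on two assumptions: that 50% is read as the nearest attainable count at or above it, and, where one method must be chosen, that it is Clopper-Pearson, the only one the documents name. The second is not needed for the result at n = 33.
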